10.6. Other Reportable Events – Pregnancy

Study center personnel must report every pregnancy on a Clinical Trial Pregnancy Form as soon as possible (within 24 business hours of learning of the pregnancy) to the email/fax number as indicated on the form, even if no AE has occurred. Pregnancies in female partners of male subjects must also be reported. The pregnancy must be followed to term and the outcome reported by completing the Clinical Trial Pregnancy Form. If, however, the pregnancy is associated with an SAE (eg, if the mother is hospitalized for hemorrhage), in addition to the Clinical Trial Pregnancy Form, a separate SAE/AESI Form for Clinical Trials must be filed as described in Section 11.1.3 with the appropriate serious criterion (eg, hospitalization) indicated on the SAE/AESI Form.

10.7. IND Safety Reports

For serious adverse events that require expedited regulatory reporting under 21 CFR 312.32(c)(1), the PI will notify the FDA in a written Investigational New Drug (IND) safety report and report to the IRB per local

10.8. Other Clinical Assessments

Safety parameters will be monitored according to standard medical practice and guidelines for IV administration of study drug. Vital sign assessments (pulse, blood pressure, respiratory rate, and temperature) will be conducted at the specified time points outlined in the Schedule of Assessments and Procedures (Table 2-1) and Section 10.0.

Medical and surgical history, prior and concomitant medications, height (length), weight, physical examination findings, and hematogenous SA osteomyelitis sign and symptom assessments will be recorded at baseline and if applicable, during study according to the Schedule of Assessments and Procedures (Table 2-1) and Section 10.0.

10.9. Laboratory Assessments

Blood samples for clinical laboratory tests and urine samples for pregnancy tests (females who have reached menarche only) will be collected at baseline and throughout the study according to the Schedule of Assessments and Procedures (Table 2-1) and Section 10.0. If a subject's estimated CrCl (as calculated using the updated Schwartz "bedside" formula; Schwartz et al, 2009) decreases to < 50 mL/min during the treatment period, the DRC should be contacted. If a subject's hemoglobin or hematocrit decreases significantly (Investigator's judgment) during IV study drug therapy, an evaluation for hemolytic anemia will be conducted per standard of care.

11. DATA MANAGEMENT

An institutional Electronic Data Capture (EDC) system, the Clinical Trials Management System (CTMS), will be used for this trial. Study specific electronic case report forms (eCRFs) designed to provide reliable and secure data entry for clinical research purposes will be utilized. The web based software tools in the CTMS employ 2048-bit Secure Socket Layer (SSL) encryption; all transactions are encrypted in both directions. The CTMS meets the regulatory requirements of HIPAA and 21 CFR Part 11 compliance. In addition, the system has an offsite, fully mirrored disaster recovery backup.

Data entered into the CTMS will include a subject study identification number; names will not be linked with subject data in the database. Study staff will maintain records linking the subject name with the identification number assigned for the study in a secure area.

All data changes in the CTMS are written to an audit trail that identifies the user, date and time, as well as the old value and new value. Both patient-related data as well as trial configuration data are written to the audit trail. Data are saved at regular intervals during data entry to prevent loss of information in the event of a disruption of the Internet connection.

The eCRFs include standard logical checks and range checks, as well as support for multiple languages in the user interface. There is emphasis on tracking deadlines and milestones with automated notifications and reports of study progress. The module includes a data locking mechanism to ensure that data accuracy and integrity are maintained to facilitate data analyses promptly after study completion. Several levels of security are employed to ensure privacy and integrity of the study data, including the following:

- Study access requires use of assigned unique user names and passwords that are modified at specified time intervals

- Individual roles and access levels are assigned
- Passwords are changed regularly
- Data are not stored on laptop computers

The study coordinator will be responsible for data entry and maintaining appropriate source documentation. Source documentation refers to original records of observations, clinical findings and evaluations that are subsequently recorded as data.

The study coordinator will enter data within 7 days of the screening visit and within 14 days of each subsequent visit.

12. STATISTICAL ASSUMPTIONS

12.1. Statistical Methods and Planned Analysis

- Descriptive statistical methods will be used to summarize the demographic characteristics of the subjects as well as selected clinical features such as duration of fever or positive blood cultures, time until normalization of ESR and CRP.
- The proportion of children with plasma concentrations of ceftaroline that exceed 1 μ g/mL at 5-6 hours following a 2 hour infusion of ceftaroline dose will be determined.
- Safety analyses will be conducted on all subjects who received at least one dose of ceftaroline.

12.2. Primary End Points

- Assessment of safety of ceftaroline in children during initial treatment of acute hematogenous osteomyelitis at the end of intravenous therapy.

12.3. Secondary Endpoints

1. Successful treatment of acute hematogenous osteomyelitis at one year after completion of a 4 to 6 week total antibiotic treatment and at one year after enrollment.
2. Clearance of *S. aureus* bacteremia if blood cultures initially positive.
3. The proportion of children with plasma concentrations of ceftaroline that exceed 1 μ g/mL for over 60% of a dosing interval.

12.4. Safety Analysis

Adverse event and serious adverse event monitoring, vital signs and laboratory tests (CBC, BUN, Creatinine, Bilirubin, Alkaline Phosphatase, AST and ALT will be obtained within 24 hours prior to enrollment and weekly during ceftaroline treatment and at the completion of ceftaroline treatment). The Alkaline Phosphatase, Bilirubin, AST/ALT results may not be available prior to enrollment of the patient.

We do not anticipate that the AST/ALT concentrations will be > 3 UNL but if they were to be this elevated, the patient subject will be dropped from the study immediately.

Safety parameters include AEs, SAEs, deaths, clinical laboratory parameters (eg, hematology parameters, chemistry parameters), and vital signs. For each safety parameter, the last assessment made before the first dose of IV study drug will be used as the baseline for all analyses.

The incidences of TEAEs, SAEs, deaths, and discontinuations due to AEs will be summarized by system organ class and preferred term according to the Medical Dictionary for Regulatory Activities by relationship to the study drug, and by severity.

Descriptive statistics of observed results and the change from baseline will be presented for clinical laboratory results, and vital signs. The incidence of PCS laboratory results will be summarized.

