No clinical chemistry or urinalysis values met potentially clinically significant (PCS) criteria. One hematology value met PCS criteria, one subject who had received several blood replacement products for blood loss secondary to trauma and surgery had a high activated partial thromboplastin time. One subject met PCS criteria for a vital sign value, a low diastolic blood pressure. Neither PCS value was associated with a TEAE. No ECG parameter values met PCS criteria. Most abnormal laboratory, vital sign, and ECG findings were consistent with the subjects' medical conditions.

These results show that a single dose of ceftaroline fosamil (8 mg/kg up to a maximum dose of 600 mg, IV) was generally well tolerated by 9 adolescent subjects who were hospitalized and receiving antibiotic therapy for an infection of any type. The mean values of maximum plasma drug concentration (Cmax) and AUC for ceftaroline observed in adolescent subjects (12 to 17 years) who received ceftaroline fosamil at a dose of 8 mg/kg (600 mg for subjects weighing > 75 kg) were approximately 10% and 23%, respectively, less than the values observed in adult subjects following administration of a 600-mg dose of ceftaroline fosamil.

Study P903-21 "Pharmacokinetics of a Single Dose of Ceftaroline fosamil in Children Ages Birth to Younger than 12 Years With Suspected or Confirmed Infection" was a Phase 1, multicenter, open-label,

sequential, single-dose, prospective study of ceftaroline fosamil. Subjects were enrolled in 5 sequential cohorts of descending age; enrollment of sequential cohorts could overlap, depending on results from intermittent PK analyses. Subjects who were hospitalized and receiving antibiotic therapy for treatment of suspected or confirmed infections were enrolled and each received a single dose of IV ceftaroline fosamil.

Data from Study P903-21, Study P903-15, and other data were used to determine the ceftaroline fosamil dose in this study.

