6.1. Outcome Measures

Primary: Safety evaluations will be conducted in the children who have started treatment with ceftaroline. Assessments will include:

- AEs, SAEs, deaths, and discontinuations due to SAEs.
- Vital signs and laboratory parameters.

Secondary:

- Clinical response (the subject has been afebrile for at least 48 hours, has negative blood cultures, is clearly improving in general, is able to eat and drink, and is able to use or move the involved extremity) at the end of parenteral therapy (approximately days 5 to 14) by subject and by baseline pathogens although *S. aureus* is expected to be the predominant pathogen.
- Clinical outcome (site of infection has complete resolution of pain, swelling and warmth and the patient is able to use the affected extremity normally and is back to normal activities) at the EOT and at the one year follow up visit.

- Clinical relapse within a year of enrollment in the study or the development of a pathologic fracture.

PK:

- Concentrations of ceftaroline fosamil, ceftaroline, and ceftaroline M-1 in plasma.
- If available, concentrations of ceftaroline fosamil, ceftaroline, and ceftaroline M-1 in purulent material such as bone or subperiosteal abscess or synovial fluid.

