9. STUDY ASSESSMENTS AND PROCEDURES

The Schedule of Assessments and Procedures is located in Table 2.1. Unless otherwise noted, the assessments and procedures should be conducted in person by the Investigator or designee.

Any protocol-required evaluations (eg, laboratory tests and) already done locally on the corresponding study day, including baseline, as part of the subject's regular medical care can be recorded on the eCRFs and do not have to be repeated for purposes of this study.

9.1.Baseline

Baseline procedures must be completed within 24 hours before the start of the first dose of IV study drug. Potential subjects who do not meet entrance criteria may, as appropriate, repeat baseline evaluations at a later time for possible enrollment into the study.

- Obtain informed consent in writing from parent(s) or legally acceptable representative(s) and assent from subject (as applicable) before initiating any study assessment or procedure.
- Collect demographic information including age, gender, race and ethnicity.
- Clinical Assessments (assessments will be performed for research unless they are already being performed per standard of care; exceptions are indicated):
 - Obtain a complete medical and surgical history, including history of surgical procedures for complications of hematogenous SA osteomyelitis (eg, drainage of the bone) and all active conditions and all conditions diagnosed within the previous 5 years (from the following categories: allergic; cardiovascular; dermatological; gastrointestinal; genital and reproductive; head, eyes, ears, nose, and throat; hematology; hepatic; immunological; metabolic and endocrine; musculoskeletal;

neurologic; psychiatric; renal; and respiratory).

- o Record prior medications (Section 8.3) taken or received within 14 days before the first dose of study drug. For children who are being breast fed, record all medications taken by the lactating mother during the 3 days before the first dose of IV study drug. In addition, record history of pneumococcal vaccinations.
- o Record standard of care radiology results.

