10.1. Adverse Events

An AE is any untoward medical occurrence in a clinical investigation subject administered a pharmaceutical product and which does not necessarily have to have a causal relationship with this treatment. An AE can therefore be any unfavorable and unintended sign (including an abnormal laboratory finding, for example), symptom, or disease temporally associated with the use of a medicinal product, whether or not considered related to the medicinal product.

Examples of AEs are as follows:

- Changes in the general condition of the subject.
- Subjective symptoms offered by or elicited from the subject.
- Objective signs observed by the Investigator or other study personnel.
- All diseases that occur after the start of the study, including any change in severity or frequency of preexisting disease.
- All clinically relevant abnormalities in laboratory values or clinically relevant physical findings that occur during the study.

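### Section 12.4 counts potentially clinically significant values for laboratory results but not for vital signs, so one child's abnormal vital sign is sure to reach the primary safety result only if it is recorded as an adverse event

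*Combined protocol and SAP*

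**What the plan says.** Section 6.1 lists "Vital signs and laboratory parameters" under the primary outcome, next to adverse events (AEs), serious AEs, deaths and discontinuations.

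Section 12.4 gives both kinds of measurement the same continuous summary: "Descriptive statistics of observed results and the change from baseline will be presented for clinical laboratory results, and vital signs". The next sentence adds a threshold-based count for one of them only: "The incidence of PCS laboratory results will be summarized". The statistics to be reported (mean, median, minimum, maximum) are not listed.

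On the reference value, Section 12.4 says that "the last assessment made before the first dose of IV study drug will be used as the baseline for all analyses". Section 9.1 sets the window: "Baseline procedures must be completed within 24 hours before the start of the first dose of IV study drug".

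Section 12.4 also plans per-child counts of events: "The incidences of TEAEs, SAEs, deaths, and discontinuations due to AEs will be summarized by system organ class and preferred term". The AE definition in Section 10.1 is wide enough to take in a vital sign: "An AE can therefore be any unfavorable and unintended sign (including an abnormal laboratory finding, for example" is how it describes the scope, and its examples include physical findings judged clinically relevant.

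Section 4.2.3, on the earlier single-dose study in nine adolescents, reports: "One subject met PCS criteria for a vital sign value, a low diastolic blood pressure. Neither PCS value was associated with a TEAE".

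**The concern.** Safety is the only primary objective, and with 18 children a safety signal is more likely to appear in an individual than in a group average. For laboratory results the plan recognises this by counting children with PCS values. For vital signs it does not, although both sit in the same line of the primary outcome and PCS criteria for vital signs were already used in the earlier adolescent study.

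The summary that remains is hard to read as evidence on safety. Baseline is measured during acute infection. Section 8.4 requires at least 48 afebrile hours before the oral switch, so temperature has to come down in children who respond, and pulse and respiratory rate plausibly follow. With no control arm, this expected movement cannot be separated from an effect of ceftaroline. A reassuring mean change would be expected from recovery alone.

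At stake is whether an isolated abnormal value in one child is visible in the primary safety tables without depending on a judgement to record it as an AE.

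**Working it through.** **Inputs from the documents.** N = 18 treated children (Sections 6.2 and 7.9). The earlier study had 1 of 9 adolescents with a PCS vital sign (Section 4.2.3). The documents give no vital-sign means, SDs or PCS limits.

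**The plan's own figure.** None is stated for vital signs. The only related figure is N = 18, from the single-stage design in Section 6.2 (0.50 against 0.80, Type 1 error 0.05, power 80%). An exact one-sided binomial check reproduces it: n = 18 with at least 13 successes gives a Type 1 error of 0.048 and power of 0.867. The designs n = 16 (at least 12; power 0.798) and n = 17 (at least 13; power 0.758) fall short. Here 18 serves only as the denominator.

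**The two measurements side by side.**

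| | Laboratory results | Vital signs |
|---|---|---|
| Primary outcome (6.1) | yes | yes |
| Descriptive statistics and change from baseline (12.4) | yes | yes |
| Incidence of PCS values (12.4) | yes | no |
| PCS values named in the minimum content for the Data Review Committee (6.4) | yes | no |

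**How far one child moves a mean.** The shift in the mean change is d/18, and its standard error is SD/√18. Both d and SD are assumptions.

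- d = 25 mmHg: 25/18 = 1.4 mmHg.
- SD = 8 mmHg: standard error 8/4.243 = 1.9 mmHg. SD = 12 mmHg: 12/4.243 = 2.8 mmHg.
- The shift is therefore 1.39/1.89 = 0.74 down to 1.39/2.83 = 0.49 standard errors.
- Wider range: d = 20 to 40 mmHg gives 1.1 to 2.2 mmHg. SD = 8 to 15 mmHg gives a standard error of 1.9 to 3.5 mmHg. The ratio runs from about 0.3 to 1.2.

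Across most of this range, one child's change is lost in the ordinary uncertainty of the mean.

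**What a count would show.** With exact (Clopper-Pearson) 95% intervals:

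- 1 of 18: 5.6% (0.1% to 27.3%).
- 0 of 18: 0% (upper limit 18.5%).

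The count makes the one child visible. It also states honestly how little a zero would exclude.

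**The case against.** The strongest reply is that the event route already works child by child. A fall in blood pressure that the investigator judges clinically relevant is an AE under Section 10.1, and Section 12.4 counts it by preferred term, relationship and severity. A reader might infer from the missing PCS count that a vital-sign harm cannot appear in the primary safety result, or that Section 12.4 would count no abnormal vital sign. The documents do not support either reading. What remains is that this route rests on judgement, with no numeric threshold, in an open-label study.

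Second, the descriptive statistics are unspecified and could include minimum and maximum, which would expose one extreme value among 18. That is fair. However, the plan does not promise them, and an extreme gives neither the number of children affected nor whether the value is abnormal for that child's age within a range of 1 to 17 years. The plan states neither pooling nor age strata, and change within a child removes much of the age difference in level.

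Third, the Data Review Committee receives individual listings of selected safety data (Section 6.4). Vital signs are neither named nor excluded there, so this is a possibility and not an assurance.

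Fourth, a reader might take the earlier study as proof that AE recording missed a harm, or project its rate onto this trial. Neither holds. Section 4.2.3 does not say that the drug caused the low pressure, and it adds that most abnormal findings fitted the subjects' medical conditions. The rate is 1/9 = 11% with an exact 95% interval of 0.3% to 48%, from a single-dose study in hospitalised adolescents with any infection. Over that interval, the chance of at least one such child among 18 runs from about 5% to nearly 100%, so it carries no useful forecast. The study shows only that a value can meet PCS criteria without an associated treatment-emergent AE.

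Finally, fever, pain and surgery will also produce abnormal values, and a shift table keeps the same acutely ill baseline. That stands as a limit on what the fix can deliver.

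**Conclusion.** The gap is real and modest. Section 12.4 plans a PCS incidence for one of two measurements that Section 6.1 places together in the primary safety outcome, and no other section supplies a count for vital signs. An abnormal value in one child is therefore assured of reaching the primary result only through an investigator-recorded AE. The change-from-baseline summary is weak on its own because recovery is expected to move temperature, and plausibly pulse and respiratory rate, in the favourable direction.

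The recovery argument concerns those three signs. For blood pressure the argument is dilution alone, and its size (0.5 to 0.7 standard errors for one child) rests on an assumed 25 mmHg fall and an assumed SD of 8 to 12 mmHg. The missing count does not depend on these assumptions. Neither the design nor the sample size is affected.

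**What to change.** In Section 12.4:

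- Extend the sentence on PCS incidence so that it covers vital signs as well as laboratory results, with age-appropriate PCS limits for each vital sign fixed before the first analysis.
- Add, for each vital sign, a shift table from baseline to the worst recorded post-dose value through the end of IV treatment, giving n/N children with an exact 95% CI.
- State that minimum and maximum are among the descriptive statistics, and keep change from baseline as supportive.
- Note in the shift table which children have no post-dose set on Day 1, because Section 9.2 allows Day 1 assessments to be skipped when dosing falls on the day of the baseline visit.

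The cost is a wording change and one extra table. Vital signs are already scheduled through treatment in Table 1.1 and Sections 9.2 to 9.4, so no visit, procedure or subject is added. The downside is that some counted values will reflect fever, pain or surgery. The table should say that it serves visibility and does not attribute values to ceftaroline.

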12.5. Efficacy Analysis

- Clinical response by subject and by baseline pathogen at the conclusion of IV ceftaroline.
- Clinical outcome at the completion of total therapy (IV plus oral)
- Clinical outcome at one year after enrollment into study long-term follow-up.

